8 LIST OF TABLES AND TABLE SHELLS

8.1 GENERAL TABLES

Table 1.1 Characteristics of the study population – 15-30 years old

	Total		Group 1	Group 2			
		Exposed	Non	P value	Exposed	Non	Р
		cohort with	exposed		cohort	exposed	value
		≥ 1 dose of	_		with ≥ 2		
		Trumemba			doses of		
					Trumemba		
All samples							
Age at vaccination							
(in years)							
Mean (SD)							
Median (Q1, Q3)							
Min, Max							
Age group (years)							
15-17							
18-19							
20-24							
25-30							
US region							
Northeast							
South							
Midwest							
West							
Unknown							
Gender							
Male							
Female							
Infection							
Gonococcal only							
Chlamydia only							
Co-infection*							

*Both the diseases occurred within 30 days of one another.

The p-values for the continuous variables were determined using Student's t-test (when the data were normally distributed as determined by Shapiro-Wilk test) or Wilcoxon-Mann-Whitney test (when the data were not normally distributed). For the normally distributed data, the p-values were derived from pooled method when the variance was equal and from Satterthwaite approximation when the variance was unequal. For the categorical variables, the p-values were determined by chi-square test (when all the cell values=10) or Fisher's exact test (when any of the cell values <10).

PFIZER CONFIDENTIAL

CT24-WI-GL03-RF03 2.0 Non-Interventional Statistical Analysis Plan For Secondary Data Collection Study 01-Jun-2020 Page 18 of 28

Table 1.2 Character		e study popula		ears old	1		
	Total		Group 1		(Group 2	
		Exposed	Non	P value	Exposed	Non	Р
		cohort (≥1	exposed		cohort (≥2	exposed	value
		dose of			doses of		
		Trumemba)			Trumemba		
Age at vaccination							
(in years)							
Mean (SD)							
Median (Q1, Q3)							
Min, Max							
Age group (years)							
16-19							
20-23							
US region							
Northeast							
South							
Midwest							
West							
Unknown							
Gender							
Male							
Female							
Infection							
Gonococcal only							
Chlamydia only							
Co-infection*							

Table 1.2 Characteristics of the study population – 16-23 years old

*Both the diseases occurred within 30 days of one another.

The p-values for the continuous variables were determined using Student's t-test (when the data were normally distributed as determined by Shapiro-Wilk test) or Wilcoxon-Mann-Whitney test (when the data were not normally distributed). For the normally distributed data, the p-values were derived from pooled method when the variance was equal and from Satterthwaite approximation when the variance was unequal. For the categorical variables, the p-values were determined by chi-square test (when all the cell values=10) or Fisher's exact test (when any of the cell values <10).

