9. RESEARCH METHODS

9.1. Study Design

This is a retrospective cohort study using health care administrative claims data as described in Section 9.4 Data Sources.

Adolescents and young adults approximately 15 to 30 years of age at their individual time zero (calculated based on birth year) will be identified from administrative claims during 01 January 2016 and 31 December 2021.

The exposure cohort will be the individuals who have received at least 1 dose of Trumenba and at least 1 dose of MenACWY (Menactra[®], Menveo[®], or MenQuadfi[®]) prior to the Trumenba vaccination, between 01 January 2016 and 31 December 2021. The index date (zero time) for the exposed cohort is the last date of vaccination, and the cohort will be followed from 14 days after vaccination to the end of the study period (31 December 2022). The individuals in the cohort will be censored by the event of interest, death date (if known), plan disenrollment (if known) or the end of the study period, whichever comes first.

PFIZER CONFIDENTIAL CT24-WI-GL02-RF02 4.0 Non-Interventional Study Protocol Template For Secondary Data Collection Study 01-Jun-2022 Page 11 of 22

The reference cohort will be those with at least 1 dose of MenACWY vaccine, but no doses of Trumemba during the observation period, received between 01January 2016 and 31 December 2021. The MenACWY-only vaccinated cohort is used as a reference cohort rather than an unvaccinated cohort in order to help control for theoretical differences in health seeking and risk behaviors between vaccinated and unvaccinated individuals. The index date (zero time) of the reference cohort is the last dose of MenACWY and these individuals will be followed from 14 days after zero time until the earliest occurrence of the following: outcome of interest, death date (if known), plan disenrollment (if known) or 31 December 2022 (end of study period).

The outcomes of interest are gonococcal and chlamydial infections and only the first episode within the study period will be considered as event in case of repeated infections.

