2.1 STUDY DESIGN

This is a retrospective cohort study including individuals 15 to 30 years of age enrolled in a health plan covered by IQVIA PharMetrics® Plus during 1 Jan 2016 to until the latest release of the data (October 2022). The study is to estimate the effect of Trumenba vaccination on the disease of interest, in particular, the gonococcal incidences will be compared between the recipients of Trumenba + MenACWY vaccines and the recipients of MenACWY vaccine.

The exposure cohort will be the individuals who have received at least one dose of Trumenba and at least one dose of MenACWY between 1 January 2016 and 31 December 2021. The non–exposure or reference cohort will be the individuals with no dose of Trumenba but at least one dose of MenACWY vaccine received during the same time period.

PFIZER CONFIDENTIAL CT24-WI-GL03-RF03 2.0 Non-Interventional Statistical Analysis Plan For Secondary Data Collection Study 01-Jun-2020 Page 4 of 28 The date of index vaccination (zero time) for the exposed cohort is the date of the last dose of Trumenba vaccination, after at least one dose of MenACWY. Trumemba and MenAWCY will be identified by Current Procedural Terminology® (CPT) codes and National Drug Codes (NDC) listed in Appendix Tables 4 and 3, respectively. The index date of the unexposed cohort is the first date of MenACWY vaccination. The diseases of interest are gonococcal infection and chlamydia infections occurring at least 14 days after the zero time. International Classification of Diseases, Tenth Revision, Clinical Modification (ICD-10-CM) codes listed in Appendix Table 1 and 2 will identify gonococcal and chlamydia infections, respectively. Only the first episode will be considered as the event in case of repeated infections. Individuals will be followed until the earliest occurrence of the following: outcome, at death date (if known), at plan disenrollment or end of study period.

Study population

This is a retrospective cohort study and the study population are adolescents and young adults approximately 15 to 30 years of age at their date of vaccination (calculated based on birth year) and will be identified from administrative claims during 01 January 2016 and 31 December 2021.

Data source

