3 HYPOTHESES AND DECISION RULES

PFIZER CONFIDENTIAL CT24-WI-GL03-RF03 2.0 Non-Interventional Statistical Analysis Plan For Secondary Data Collection Study 01-Jun-2020 Page 6 of 28 This is an exploratory study, thus no hypothesis will be tested. There will be more than 500,000 individuals in which approximately 15% will be the experimental group. Assming a total of 500,000 subjects, and the probability of failure in the experimental group over the maximum time period of the study is 0.0036 and the probability of failure in the control group over the maximum time period of the study is 0.0048. This provides a power of 94% assuming a hazard ratio of 80% (20% vaccine effectiveness) and at an alpha of 0.05. The calculation was made using "powerSurvEPI" package under RStudio (Version 1.1.453).

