7 STATISTICAL METHODOLOGY AND STATISTICAL ANALYSES

7.1 STATISTICAL METHODS

Means, medians, and standard deviations will be provided for continuous variables when performing descriptive analysis of continuous data. Numbers and percentages will be provided for dichotomous and polychotomous variables when performing descriptive analysis of categorical data. Bivariate comparisons of baseline characteristics and outcomes measures will be provided. Appropriate tests (e.g., t-test, chi-square test) will be used based on the distribution of the measure. The cumulative incidence rate for clinical outcomes will be calculated. The incidence rate will be calculated as the number of patients who experience the event divided by the observed time at risk. An unadjusted Kaplan Meier curve will be drawn to illustrate time-to-event.

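### SAP Tables 1.1 and 1.2 attach chi-square or Fisher p-values to infection outcomes on head counts, although follow-up is not equalised between the cohorts

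*SAP*

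**What the plan says.** SAP section 7.1 states: "Bivariate comparisons of baseline characteristics and outcomes measures will be provided". The next sentence names the tests: "Appropriate tests (e.g., t-test, chi-square test) will be used based on the distribution of the measure".

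Tables 1.1 (15-30 years) and 1.2 (16-23 years) in SAP section 8.1 are titled as tables of population characteristics. Each also has an Infection block with three rows: gonococcal only, chlamydia only and co-infection. The block sits under the same P value columns as age, region and gender, once for the one-dose comparison and once for the two-dose comparison. The footnote to each table reads "For the categorical variables, the p-values were determined by chi-square test", with Fisher's exact test for small cells, and exempts no row.

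Zero time for the exposed cohort is "the date of the last dose of Trumenba vaccination, after at least one dose of MenACWY" (SAP 2.1). For the reference cohort the two documents differ:
- SAP 2.1: "The index date of the unexposed cohort is the first date of MenACWY vaccination".
- Protocol 9.1: "The index date (zero time) of the reference cohort is the last dose of MenACWY".

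In both documents, outcome follow-up starts 14 days after zero time. It ends at the outcome, death, disenrollment or the study end, whichever is first.

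Elsewhere the plan does account for time at risk. SAP 7.2.1.1 uses Cox models that allow for staggered entry. Tables 2.1, 3.1 and 3.2 report cases, person-years, rates and VE.

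**The concern.** A chi-square or Fisher test of infected versus not infected compares the share of people who ever became a case. That share depends on the hazard and on how long each person was observed. The two cohorts start their clocks at different kinds of event, and neither version of the reference zero time equalises follow-up. A difference in head counts can therefore arise with no vaccine effect.

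These p-values would sit in the first results tables of a study that uses a two-sided alpha of 0.05 with no multiplicity adjustment (SAP 3.2). They would be unadjusted for age, sex and region. They would also cover chlamydia, which protocol 9.9 uses as the reference outcome for detecting residual confounding. A reader could find a small p-value in Table 1.1 beside a person-time result in Table 2.1 that points elsewhere.

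**Working it through.** **Inputs from SAP section 3.** N = 500,000 with about 15% exposed, giving 75,000 v 425,000. Failure probabilities are 0.0036 (exposed) and 0.0048 (reference), the hazard ratio (HR) is 0.80 and the stated power is 94%.

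**The plan's own figure.** Expected events are 75,000 × 0.0036 + 425,000 × 0.0048 = 270 + 2,040 = 2,310. With k = 75,000/425,000 = 0.1765, a Freedman-type formula gives power = Φ(√(k × 2,310) × 0.20/(0.80k + 1) − 1.96) = Φ(3.54 − 1.96) = 94.3%. This reproduces the 94%, so these sizes and risks are a fair base. The documents give no figure for the Table 1.1 and 1.2 p-values themselves.

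**Head-count test when the true HR is 1.** Let r be mean exposed follow-up divided by mean reference follow-up. The documents do not give r, so it is varied.
- p0 = reference risk, and p1 = 1 − (1 − p0)^r.
- d = p1 − p0, and p̄ = (75,000 p1 + 425,000 p0)/500,000.
- SE0 = √[p̄(1 − p̄)(1/75,000 + 1/425,000)].
- SE1 = √[p1(1 − p1)/75,000 + p0(1 − p0)/425,000].
- Rejection probability = Φ((−1.96 SE0 − d)/SE1) + 1 − Φ((1.96 SE0 − d)/SE1).

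Example with r = 0.90 and p0 = 0.0048: p1 = 0.004321, d = −0.000479, SE0 = 0.0002717 and SE1 = 0.0002619. The lower tail is Φ(−0.204) = 0.419 and the upper tail is negligible.

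The 0.0048 is the planning risk for any gonococcal infection. The row is gonococcal only, whose risk must be lower if co-infections are removed, so half that risk is shown as an assumed alternative.

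| r | Risk 0.0048 | Risk 0.0024 |
|---|---|---|
| 1.00 | 5.0% | 5.0% |
| 0.95 | 13.7% | 9.1% |
| 0.90 | 41.9% | 23.0% |
| 0.85 | 76.9% | 46.5% |
| 0.80 | 95.7% | 72.5% |
| 1.10 | 41.4% | 24.0% |

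The last row shows exposed follow-up 10% longer. The error is then of similar size in the opposite direction.

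**What r might be under the SAP's zero-time rule.** This simulation assumes MenACWY dates uniform over 2016-2021, study end at the end of 2022, a reference risk of 0.0048 and true HR = 1. The gap from MenACWY to last Trumenba dose is uniform from 0 to the stated maximum, and disenrollment is exponential. All gap and disenrollment values are assumptions. Cells show r and the head-count rejection rate (20,000 simulated tables each).

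| Maximum gap | No disenrollment | Mean 3 years | Mean 1.5 years |
|---|---|---|---|
| 0.5 y | 0.970, 7.8% | 0.988, 5.4% | 0.992, 5.3% |
| 1 y | 0.939, 18.8% | 0.976, 7.1% | 0.989, 5.4% |
| 2 y | 0.884, 53.3% | 0.945, 16.0% | 0.978, 6.3% |
| 4 y | 0.790, 97.0% | 0.886, 51.9% | 0.945, 15.4% |

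A test on events per person-time stayed between 4.8% and 5.2% in all twelve scenarios.

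**The alternative reading of the block.** The shell has no row for people without infection. The block could therefore be tested as one three-level variable among cases. With row risks of 0.0036, 0.012 and 0.0012 (assumed) and HR = 1, simulated rejection was about 5% at r = 0.90 and at r = 0.80. That test is not distorted by uniformly shorter follow-up, but it compares only the mix of infection types and says nothing about vaccine effect.

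**The case against.** The strongest reply is that the P value cells are blank in the shells, so how the block would be tested is an inference. That stands. The shared column, the unrestricted footnote and section 7.1 all point to a test of the outcomes, but do not say whether it is row by row or one test of three levels. The first is distorted by follow-up and the second is uninformative about VE, so neither belongs in the table.

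It is also fair that the ratio r is not in the documents, and that disenrollment shrinks the imbalance, in some scenarios to almost nothing. The results are therefore a range, including the near-nominal end.

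A third reply is that outcomes are already handled properly. Cox regression is the stated method, Table 2.1 carries person-years and unadjusted and adjusted VE, the appendix code for the Kaplan-Meier curves requests a log-rank test, and no decision rests on the Table 1 p-values. This limits the harm and makes the repair easy, but it does not make the head-count p-values valid.

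Three stronger readings are tempting but unsupported:
- A reader might infer that the p-values must favour Trumenba. The SAP's zero-time rule suggests shorter exposed follow-up but does not guarantee it, and the protocol starts reference follow-up at the last MenACWY dose, which changes the size of the imbalance.
- A reader might take the SAP's planning risks as proof of the artefact, because "the probability of failure in the experimental group over the maximum time period of the study is 0.0036" against 0.0048 gives z = −4.47. Those risks accompany an assumed HR of 0.80, and equal follow-up with that HR already gives z = −3.55. Most of the z is the assumed vaccine effect.
- A reader might infer that the two 'only' rows overlap. The co-infection footnote says "Both the diseases occurred within 30 days of one another", and no rule covers a person with both infections further apart. That leaves the category undefined; it does not show that the person is counted twice.

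**Conclusion.** The point holds in a limited form. As written, the SAP calls for head-count tests of infection outcomes between cohorts whose follow-up is not equalised. If each row is tested as infected versus not, the type I error for a vaccine effect is not controlled. Under the SAP's sample sizes and the assumed risks and follow-up ratios above, it runs from about 5% to over 95%, and the documents do not allow a narrower figure. The result assumes a constant hazard and rests on the row-by-row reading.

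The primary and secondary VE estimates, which come from Cox models, are not affected. A reader might infer that the study's conclusions on VE are compromised, but nothing here supports that. What is at stake is a set of invalid descriptive p-values, including for the chlamydia reference outcome, that could contradict Table 2.1.

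**What to change.** In SAP 7.1, take outcome measures out of the sentence on bivariate comparisons, or state that outcomes are compared between cohorts only by person-time methods. In Tables 1.1 and 1.2, remove the P value from the Infection rows. The counts may stay, with a note referring the reader to Table 2.1, which already provides for cases, person-years, rates and unadjusted VE with 95% confidence intervals.

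The cost is SAP wording and two table shells. No new data or analysis is needed.

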8.2 TABLES – PRIMARY AND SECONDARY ENDPOINTS

		ort		Non-Ex	Unadjusted	Adjusted				
	No. of	Person	Cases	Incidence/	No. of	Person	Cases	Incidence/	VE (95%	VE
	persons	years		100,000/year	persons	years		100,000/year	CI)	(95%
										CI)
≥ 1 dose of T	rumenba									
Gonococcal							******	****	XX	XX
infection	XX	XX	XXXX	XX.XX	XX	XX	XXXX	XX.XX	(xx, xx)	(xx, xx)
Gonococcal									XX	XX
infection	XX	XX	XXXX	XX.XX	XX	XX	XXXX	XX.XX	(xx, xx)	(xx, xx)
only										
Chlamydial	xx	xx	XXXX	XX.XX	xx	xx	vvvv	XX.XX	XX	XX
infection	лл	лл	лллл	ΛΛ.ΛΛ	лл	лл	XXXX	ΛΛ.ΛΛ	(xx, xx)	(xx, xx)
Chlamydial									XX	XX
infection	XX	XX	XXXX	XX.XX	XX	XX	XXXX	XX.XX	(xx, xx)	(xx, xx)
only										
≥ 2 doses of 2	Frumenb	a							•	
Gonococcal	xx	xx	XXXX	XX.XX	xx	xx	XXXX	XX.XX	XX	XX
infection	лл	лл	лллл	ΛΛ.ΛΛ	лл	лл	ΛΛΛΛ	ΛΛ.ΛΛ	(xx, xx)	(xx, xx)
Gonococcal									XX	XX
infection	XX	XX	XXXX	XX.XX	XX	XX	XXXX	XX.XX	(xx, xx)	(xx, xx)
only										
Chlamydial	VV	VV	VVVV	VV VV	VV	VV	VVVV	VV VV	XX	XX
infection	XX	XX	XXXX	XX.XX	XX	XX	XXXX	XX.XX	(xx, xx)	(xx, xx)
Chlamydial									XX	XX
infection	XX	XX	XXXX	XX.XX	XX	XX	XXXX	XX.XX	(xx, xx)	(xx, xx)
only										

VE calculated as 1 minus the hazard ratio for gonococcal infection between exposed and non-exposed cohort, multiplied by 100

PFIZER CONFIDENTIAL CT24-WI-GL03-RF03 2.0 Non-Interventional Statistical Analysis Plan For Secondary Data Collection Study 01-Jun-2020 Page 20 of 28

8.3 TABLES – EXPLORATORY ENDPOINTS

		Exposed cohort				Non-E	Exposed co	ohort	Unadjusted	Adjusted
	No. of persons	No. of cases	Person- years	Incidence/ 100,000/year	No. of persons	No. of cases	Person- years	Incidence/ 100,000/year	VE (95% CI)	VE (95% CI)
≥ 1 dose of T	rumenba	1	1	1	1	r	1	1	I	
Gonococcal infection	XX	xx	xxxx	XX.XX	XX	xx	xxxx	XX.XX	xx (xx, xx)	XX (XX, XX)
Gonococcal infection only	xx	XX	xxxx	xx.xx	xx	XX	xxxx	xx.xx	xx (xx, xx)	XX (XX, XX)
Chlamydial infection	XX	XX	xxxx	xx.xx	XX	XX	xxxx	xx.xx	XX (XX, XX)	xx (xx, xx)
Chlamydial infection only	xx	xx	xxxx	xx.xx	xx	XX	xxxx	xx.xx	XX (XX, XX)	xx (xx, xx)
≥ 2 doses of $[$	[[] Frumenb	a								
Gonococcal infection	xx	xx	xxxx	xx.xx	XX	XX	xxxx	xx.xx	xx (xx, xx)	xx (xx, xx)
Gonococcal infection only	xx	XX	xxxx	xx.xx	xx	XX	xxxx	XX.XX	xx (xx, xx)	XX (XX, XX)
Chlamydial infection	XX	XX	xxxx	xx.xx	XX	xx	xxxx	xx.xx	XX (XX, XX)	$\begin{array}{c} \mathbf{x}\mathbf{x}\\ (\mathbf{x}\mathbf{x},\mathbf{x}\mathbf{x}) \end{array}$
Chlamydial infection only	xx	xx	xxxx	XX.XX	xx	xx	xxxx	XX.XX	xx (xx, xx)	xx (xx, xx)

Table 3.1. Effectiveness of Trumenba in 16-23 Years Old

VE calculated as 1 minus the hazard ratio for gonococcal infection between exposed and non-exposed cohort, multiplied by 100

PFIZER CONFIDENTIAL CT24-WI-GL03-RF03 2.0 Non-Interventional Statistical Analysis Plan For Secondary Data Collection Study 01-Jun-2020 Page 21 of 28

Table 3.2 Effectiveness of Trumenba in 15-30 Years by Year of Follow-up Among Participants received ≥1 dose of Truumenba

		Me	enACWY	only	T	RUMEN	NBA and N	MenACWY	Unadjusted VE		Adjusted VE	
	No. of persons	No. of cases	Person- years	Incidence/ 100,000/year	No. of persons	No. of cases	Person- years	Incidence/ 100,000/year	VE	95% CI	VE	95% CI
At 12 months	of follow	v-up			1	1	1		1	1		
Gonococcal infection	XX	xx	xxxx	xx.xx	XX	XX	XXXX	XX.XX	xx	xx, xx	XX	xx, xx
Chlamydial infection	XX	XX	xxxx	XX.XX	XX	XX	XXXX	XX.XX	xx	xx, xx	XX	xx, xx
At 24 months	of follow	v-up										
Gonococcal infection	XX	XX	xxxx	XX.XX	xx	XX	XXXX	XX.XX	xx	xx, xx	XX	xx, xx
Chlamydial infection	xx	XX	xxxx	xx.xx	xx	XX	xxxx	XX.XX	xx	xx, xx	XX	xx, xx
At 36 months	of follow	v-up			1	I.				1		
Gonococcal infection	XX	XX	xxxx	xx.xx	XX	XX	XXXX	XX.XX	xx	xx, xx	XX	xx, xx
Chlamydial infection	XX	XX	xxxx	XX.XX	XX	XX	XXXX	XX.XX	xx	xx, xx	XX	xx, xx
At 48 months	of follow	v-up										
Gonococcal infection	XX	XX	xxxx	XX.XX	XX	XX	XXXX	XX.XX	XX	xx, xx	XX	xx, xx
Chlamydial infection	XX	XX	xxxx	XX.XX	xx	XX	xxxx	XX.XX	XX	xx, xx	XX	xx, xx

VE calculated as 1 minus the hazard ratio for gonococcal infection between exposed and non-exposed cohort, multiplied by 100

PFIZER CONFIDENTIAL CT24-WI-GL03-RF03 2.0 Non-Interventional Statistical Analysis Plan For Secondary Data Collection Study 01-Jun-2020 Page 22 of 28

9 LIST OF FIGURES

- 9.1 FIGURE 1. KAPLAN-MEIER SURVIVAL CURVE FOR NOT HAVING GONOCOCCAL INFECTION AMONG PARTICIPANTS RECEIVED AT LEAST ONE DOSE OF TRUMENBA
- 9.2 FIGURE 2. KAPLAN-MEIER SURVIVAL CURVE FOR NOT HAVING GONOCOCCAL INFECTION AMONG PARTICIPANTS RECEIVED AT LEAST TWO DOSES OF TRUMENBA
- 9.3 FIGURE 1. KAPLAN-MEIER SURVIVAL CURVE FOR NOT HAVING CHLAMYDIAL INFECTION AMONG PARTICIPANTS RECEIVED AT LEAST ONE DOSE OF TRUMENBA
- 9.4 FIGURE 2. KAPLAN-MEIER SURVIVAL CURVE FOR NOT HAVING CHLAMYDIAL INFECTION AMONG PARTICIPANTS RECEIVED AT LEAST TWO DOSES OF TRUMENBA

10 APPENDICES

10.1 APPENDIX 1: DATA DERIVATION DETAILS

Age in years will be calculated in years as integer ((Date of vaccination - Date of Birth + 1) /365.25). Since the date of birth is written in year only, we will add July 1 of the year as the data of birth of the individuals.

10.2 APPENDIX 2: ADDITIONAL STATISTICAL METHODOLOGY DETAILS

10.2.1 Procudure for producing the KM Curve

Proc lifetest data=ana outtest=test maxtime=2500 outsurv=surv noprint; time time*event(0); strata exposure/test=logrank;run; symbol1 i=join c=black v=none; symbol2 i=join c=red v=none; title h=1 "Kaplan-Meier Survival Curve of Not Having Gonoccoal Infection"; proc gplot data=surv; plot survival*time=exposure; run;

10.3 APPENDIX 3: DIAGNOSIS AND PROCEDURE CODES USED IN THE STUDY

Code	Туре
A540	ICD-10-CM
A5400	ICD-10-CM
A5401	ICD-10-CM

Table 1. Diagnosis Codes for Identifying Gonococcal Infections

PFIZER CONFIDENTIAL CT24-WI-GL03-RF03 2.0 Non-Interventional Statistical Analysis Plan For Secondary Data Collection Study 01-Jun-2020 Page 24 of 28

A5402	ICD-10-CM
A5403	ICD-10-CM
A5409	ICD-10-CM
A541	ICD-10-CM
A542	ICD-10-CM
A5421	ICD-10-CM
A5422	ICD-10-CM
A5423	ICD-10-CM
A5424	ICD-10-CM
A5429	ICD-10-CM
A543	ICD-10-CM
A5430	ICD-10-CM
A5431	ICD-10-CM
A5432	ICD-10-CM
A5433	ICD-10-CM
A5439	ICD-10-CM
A544	ICD-10-CM
A5440	ICD-10-CM
A5441	ICD-10-CM
A5442	ICD-10-CM
A5443	ICD-10-CM
A5449	ICD-10-CM
A545	ICD-10-CM
A546	ICD-10-CM
A548	ICD-10-CM
A5481	ICD-10-CM
A5482	ICD-10-CM

PFIZER CONFIDENTIAL CT24-WI-GL03-RF03 2.0 Non-Interventional Statistical Analysis Plan For Secondary Data Collection Study 01-Jun-2020 Page 25 of 28

A5483	ICD-10-CM
A5484	ICD-10-CM
A5485	ICD-10-CM
A5486	ICD-10-CM
A5489	ICD-10-CM
A549	ICD-10-CM

Table 2. Diagnosis Codes for Identifying Chlamydial Infections

Code	Туре
A55	ICD-10-CM
A560	ICD-10-CM
A5600	ICD-10-CM
A5601	ICD-10-CM
A5602	ICD-10-CM
A5609	ICD-10-CM
A561	ICD-10-CM
A5611	ICD-10-CM
A5619	ICD-10-CM
A562	ICD-10-CM
A563	ICD-10-CM
A564	ICD-10-CM
A568	ICD-10-CM
A71	ICD-10-CM
A710	ICD-10-CM
A711	ICD-10-CM
A719	ICD-10-CM

PFIZER CONFIDENTIAL CT24-WI-GL03-RF03 2.0 Non-Interventional Statistical Analysis Plan For Secondary Data Collection Study 01-Jun-2020 Page 26 of 28

A74	ICD-10-CM
A740	ICD-10-CM
A748	ICD-10-CM
A7481	ICD-10-CM
A7489	ICD-10-CM
A749	ICD-10-CM

Table 3. Current Procedural Terminal Codes and National Drug Codes for Identifying MenACWY Vaccination

Code	Туре	Description
90734	СРТ	Menactra/Menveo Vaccination
90619	СРТ	Menquadfi Vaccine
49281-0589-05	NDC	Menactra Vaccine
46028-0208-01	NDC	Menveo Vaccine
58160-0955-09	NDC	Menveo Vaccine
49281-0589-58	NDC	Menactra Vaccine
49281-0590-58	NDC	Menquadfi Vaccine
46028-0218-11	NDC	Menveo Vaccine
58160-0958-01	NDC	Menveo Vaccine
58160-0959-01	NDC	Menveo Vaccine
46028-0219-11	NDC	Menveo Vaccine
54569-5687-01	NDC	Menactra Vaccine
50090-1890-01	NDC	Menactra Vaccine
49281-0590-05	NDC	Menquadfi Vaccine

Table 4. Current Procedural Terminal Codes and National Drug Codes for Identifying Trumemba (fHbp) Vaccination

PFIZER CONFIDENTIAL CT24-WI-GL03-RF03 2.0 Non-Interventional Statistical Analysis Plan For Secondary Data Collection Study 01-Jun-2020 Page 27 of 28

Code	Туре	Description
90621	СРТ	Trumenba Vaccination
00005-0100-01	NDC	Trumenba Vaccine
00005-0100-02	NDC	Trumemba Vaccine
00005-0100-05	NDC	Trumenba Vaccine
00005-0100-10	NDC	Trumenba Vaccine

Table 5. Current Procedural Terminal Codes and National Drug Codes for Identifying Bexsero 4CMenB Vaccination

Code	Туре	Description
90620	-CPT	Meningococcal recombinant
		protein and outer membrane
		vesicle (OMV) vaccine,
		serogroup B (MenB-4C), 2
		dose schedule, for
		intramuscular use
46028011401	NDC	Bexsero vaccine
46028011402	NDC	Bexsero vaccine
46028011411	NDC	Bexsero vaccine
58160097602	NDC	Bexsero vaccine
58160097606	NDC	Bexsero vaccine
58160097620	NDC	Bexsero vaccine

PFIZER CONFIDENTIAL CT24-WI-GL03-RF03 2.0 Non-Interventional Statistical Analysis Plan For Secondary Data Collection Study 01-Jun-2020 Page 28 of 28
